6.4. Visit 4 – Test Irradiation (UV Exposure)

6.4.1. Concomitant Medication

Any concomitant therapy taken since the last visit and throughout the study will be recorded on the CRF by the Investigator or medically qualified designee.

6.4.2. Continued Eligibility

The Investigator or designee will ascertain whether there have been any deviations from the protocol since the last visit, whether the subject has adhered to the lifestyle restrictions since the last visit and whether, in their opinion, the subject is eligible to continue in the study and their decision will be documented on the CRF.

 GlaxoSmithKline	Document Name	207640 Protocol.doc		
	Type	Version	Document Identifier	Effective Date
	eldo_controlled	2.0; Most-Recent; Effective; CURRENT	090032d580d3df08	11-May-2017 13:45:31
	Reason For Issue	Auto Issue		

6.4.3. Study Product Application to Randomly Assigned Test Sites on the Back

Test sites intended for UV exposure shall be free from blemishes and have an even colour tone. The total area for test site study product application will be 40 cm². Test site demarcation, product application, UV exposures and MED assessments will be conducted in stable conditions with the subject lying horizontally on their front and in a room with controlled temperature (22 ± 4 °C).

The positions of the test product, reference sunscreen and unprotected test sites will be randomised over the whole group in order to reduce error arising from anatomical differences in skin. There will be a minimum distance of 1 cm between the borders of adjacent test sites to ensure no overlap of product and UV exposure. Prior to product application, the test site may be cleaned using a dry cotton pad or equivalent. The test sites will be delineated by a method which does not interfere with the procedures or assessments or harm the subject, using a skin marker and template made from non-absorbent material. Test sites will not overlap with the site previously used for the provisional MEDu assessment.

The amount of test product and reference sunscreen formulation applied to the skin before spreading will be 2.00 ± 0.05 mg / cm² (i.e. 78.0 – 82.0 mg, inclusive). The balance used to weigh the products must be calibrated and capable of weighing to the nearest 0.0001 grams (g) (i.e. to the nearest 0.1 mg). All products will be homogeneous and will be shaken before weighing to ensure uniform dispersion.

When handling the product during weighing or before application to the skin, appropriate measures will be taken to prevent evaporative loss of the volatile components. In particular, study staff will apply the test product to subjects immediately after weighing and the containers filled with product will remain sealed when not in use.

The amount of product to be applied will be weighed in a syringe. The syringe will be loaded with sufficient product to deliver 2.00 ± 0.05 mg / cm² to the test site and weighed alongside a new, unsaturated finger cot. The syringe will then be evacuated directly on to the test site. To aid uniform coverage, droplets (approximately 20) of the product will be deposited within the test site, then spread over the whole test site using the weighed finger cot, applying a light pressure. The spreading time will be in the range of 35 ± 15 seconds. Once spreading is complete, the used finger cot and evacuated syringe will be weighed again and the total mass of applied product calculated and recorded. If the mass of total applied product is less than 78.0 mg or greater than 82.0 mg the test site will not undergo UV exposure. If there is sufficient space on the subject's back, between the scapula line and waist, a new 40 cm² site will be demarcated and will be positioned at least 1 cm from the borders of the other four test sites. The new test site will only undergo UV exposure if the total mass of

 GlaxoSmithKline	Document Name	207640 Protocol.doc		
	Type	Version	Document Identifier	Effective Date
	eldo_controlled	2.0; Most-Recent; Effective; CURRENT	090032d580d3df08	11-May-2017 13:45:31
	Reason For Issue	Auto Issue		

applied product is 78.0 to 82.0 mg, inclusive. If there is insufficient space on the subject's back to accommodate the test product, positive control and unprotected sites then the subject will not undergo any UV exposure and they will be discontinued from further participation in the study.

6.4.4. UV Exposure of Test Product Treated, Reference Sunscreen Formulation Treated and Unprotected Test Sites

The specification of the solar simulator output is included in Appendix 3. A UV dose is the result of multiplying the UV source irradiance by the episode duration. In this study, a solar simulator with 6 light guides exposing all sub-sites for the same duration but with varied irradiance values will be used. Before UV exposure of each test site, irradiance values will be measured and recorded with a radiometer which has been calibrated with a spectroradiometric measurement of the solar simulator output.

A suitable warm-up time of at least 10 minutes will be allowed for the UV solar simulator to stabilize before starting exposures. This is to ensure a consistent irradiance over the whole exposure period. Irradiation procedures will be conducted with the subject lying horizontally on their front and in a room with controlled temperature (22 ± 4 °C).

The minimum area of each exposure sub-site will be 0.5 cm^2 . The minimum distance between borders of each exposure sub-site (spots) will be at least 0.8 cm. The distance between any exposure sub-site and any edge of the test site will be at least 1 cm.

Exposure of the test site to UV radiation will start 15 to 30 minutes after the application of the test product. Exposure of the positive control site to UV radiation will start 15 to 30 minutes after application of the positive control. Exposure of the unprotected site to UV radiation may happen at any point after demarcation of the test sites and after the 10 minutes required for the solar simulator to warm up. Exposure of the unprotected site, positive control and test product sites will be conducted sequentially, in any order, on same subject on the same day.

For the unprotected site, the range of UV doses administered shall be selected using the subject's provisional MED_u. Six exposure sub-sites centered on the provisional MED_u shall be exposed with incremental UV doses using a geometric progression of 1.25. The dose of UV radiation administered to subjects will be chosen such that the provisional MED_u will be irradiated on the 4th of the 6 sub-sites.

For the test product and reference formulation protected sites, the UV doses administered shall be selected using the subject's expected MED_p, which is the multiple of the expected SPF of the study product and the provisional MED_u for the subject. A minimum of 6 sub-sites centered on the expected MED_p shall be exposed

 GlaxoSmithKline	Document Name	207640 Protocol.doc		
	Type	Version	Document Identifier	Effective Date
	eldo_controlled	2.0; Most-Recent; Effective; CURRENT	090032d580d3df08	11-May-2017 13:45:31
	Reason For Issue	Auto Issue		

with incremental UV doses using a geometric progression of 1.25. The dose of UV radiation administered to subjects will be chosen such that the expected MEDp will be irradiated on the 4th of the 6 sub-sites. After the UV exposure procedures are complete, reference and test product may be gently removed by wiping with a dry tissue.

Any extraneous exposure of the test sites to UV light (artificial or natural) will be avoided during this period and until visual evaluation is completed. Any additional UV exposure to the test area will invalidate the whole test for the subject concerned.

6.4.5. Adverse Events

Adverse events will be assessed by the Investigator or designee and recorded on the CRF, as per the process detailed in Section 7. Localised erythema caused by exposure of the skin to UV radiation is expected and will not be reported as an adverse event.

6.5. Visit 5 – MEDp and MEDu Determination and SPF Calculation for Test and Reference Sunscreen

6.5.1. Concomitant Medication

Any concomitant therapy taken since the last visit and throughout the study will be recorded on the CRF by the Investigator or medically qualified designee.

6.5.2. Continued Eligibility

The Investigator or designee will ascertain whether there have been any deviations from the protocol since the last visit, whether the subject has adhered to the lifestyle restrictions since the last visit and whether, in their opinion, the subject is eligible to continue in the study and their decision will be recorded on the CRF.

6.5.3. Visual Grading of Exposure Sub-Sites to Determine MEDp and MEDu

The MED is defined as the lowest dose of UV radiation that produces the first perceptible unambiguous erythema with defined borders appearing over most of the field of UV exposure, 16 to 24 hours after UV exposure.

The MED determination will be assessed visually by a trained grader with the subject lying horizontally on their front in a room with controlled temperature (22 ± 4 °C). The same grader will assess all subjects in the study. The grader's eyesight must have been checked for normal colour vision and acuity within the previous year. Visual assessment will be performed in a room with matt, neutral wall colours with sufficient and uniform illumination. Erythematous responses will be observed in a blind manner. The grader must not be the same person as the one who performed product

 GlaxoSmithKline	Document Name	207640 Protocol.doc		
	Type	Version	Document Identifier	Effective Date
	eldo_controlled	2.0; Most-Recent; Effective; CURRENT	090032d580d3df08	11-May-2017 13:45:31
	Reason For Issue	Auto Issue		

application and exposure nor will the grader be aware of the test design (randomisation of test sites) for any subject.

The MEDu and MEDp values for each subject will be recorded on the CRF with units of mJ/cm².

6.5.4. Adverse Events

Adverse events will be assessed by the Investigator or designee and recorded on the CRF, as per the process detailed in Section 7. Localised erythema caused by exposure of the skin to UV radiation is expected and will not be reported as an adverse event.

6.5.5. Study Conclusion

Subjects will be evaluated to determine if they completed all study procedures or if they were discontinued from the study early. If the subject discontinued at any point during the study, the primary reason for withdrawal should be recorded on the Study Conclusion page of the CRF by selecting one of the options below.

1. Subject did not meet study criteria
2. Adverse Event
3. Lost to Follow Up
4. Protocol Violation
5. Withdrawal of Consent
6. Other

 GlaxoSmithKline	Document Name	207640 Protocol.doc		
	Type	Version	Document Identifier	Effective Date
	eldo_controlled	2.0; Most-Recent; Effective; CURRENT	090032d580d3df08	11-May-2017 13:45:31
	Reason For Issue	Auto Issue		

7. SAFETY ASSESSMENTS

7.1. Definitions of an Adverse Event and Serious Adverse Event

7.1.1. Adverse Events

The investigator or site staff will be responsible for detecting, documenting and reporting events that meet the definition of an AE or SAE.

Adverse Event Definition:

1. An AE is any untoward medical occurrence in a patient or clinical investigation subject, temporally associated with the use of an investigational or washout product, whether or not considered related to the investigational or washout product.
2. NOTE: An AE can therefore be any unfavorable and unintended sign (including an abnormal laboratory finding), symptom, or disease (new or exacerbated) temporally associated with the use of an investigational or washout product.

Events meeting AE definition include:

1. Any abnormal laboratory test results (if applicable) or other safety assessments, including those that worsen from baseline, and felt to be clinically significant in the medical and scientific judgment of the investigator.
2. Exacerbation of a chronic or intermittent pre-existing condition including either an increase in frequency and/or intensity of the condition.
3. New condition(s) detected or diagnosed after study product administration even though it may have been present prior to the start of the study.
4. Signs, symptoms, or the clinical sequelae of a suspected interaction.
5. Signs, symptoms, or the clinical sequelae of a suspected overdose of either study product or a concomitant medication (overdose per se will not be reported as an AE/SAE).

Events NOT meeting definition of an AE include:

1. Any clinically significant abnormal laboratory findings (if applicable) or other abnormal safety assessments which are associated with the underlying disease, unless judged by the investigator to be more severe than expected for the subject's condition.
2. The disease/disorder/ condition being studied or expected progression, signs, or symptoms of the disease/disorder being studied, unless more severe than expected for the subject's condition..
3. Medical or surgical procedure (e.g., endoscopy, appendectomy): the condition that leads to the procedure is an AE.

 GlaxoSmithKline	Document Name	207640 Protocol.doc		
	Type	Version	Document Identifier	Effective Date
	eldo_controlled	2.0; Most-Recent; Effective; CURRENT	090032d580d3df08	11-May-2017 13:45:31
	Reason For Issue	Auto Issue		

4. Situations where an untoward medical occurrence did not occur (social and/or convenience admission to a hospital).
5. Anticipated day-to-day fluctuations of pre-existing disease(s) or condition(s) present or detected at the start of the study that do not worsen.
6. Localised erythema caused by exposure of the skin to UV radiation.

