2. OBJECTIVE(S) AND ENDPOINT(S)

Objective(s)	Endpoint(s)
Primary	
To determine the Sun Protection Factor of the test product	Arithmetical mean of all valid individual sun protection factor (SPFi) values; where $SPFi = \frac{\text{Minimal Erythematous Dose of product treated (MEDp)}}{\text{Minimal Erythematous Dose of unprotected (MEDu) test sites}}$ in relation to unprotected (MEDu) test sites 16-24 hours after exposure to ultraviolet (UV) radiation.
To evaluate the general safety of the test product	Frequency and severity of Adverse Events

 GlaxoSmithKline	Document Name	207640 Protocol.doc		
	Type	Version	Document Identifier	Effective Date
	eldo_controlled	2.0; Most-Recent; Effective; CURRENT	090032d580d3df08	11-May-2017 13:45:31
	Reason For Issue	Auto Issue		

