9.2.2. Exclusion of Data from Analysis

Test data are deemed invalid and shall be rejected under the following circumstances:

- The series of UV exposures on a subject fails to elicit an erythematous response on any sub-site, 16-24 hours after exposure.
- Erythematous responses within an exposure series are randomly absent 16-24 hours after exposure.
- All sub-sites in the exposure series show an erythematous response 16-24 hours after exposure.

When one of the above criteria applies to the exposure of unprotected skin, test product or reference sunscreen formulation exposure sites, then all data for all products on that subject are invalid and shall be rejected. If data have to be rejected for the unprotected skin, test product or reference sunscreen formulation on more than five subjects, then the whole test is invalid and shall be rejected.

Any additional exposure of a test area to natural or artificial UV radiation will invalidate the whole test for that subject.

Major violations will be identified and any exclusion of subject data justified. Data deemed invalid due to protocol violations which are not related to the UV exposure procedures, such as illness, equipment failure, and subject drop out will not be included in analysis of efficacy and will not count towards the maximum of 5 invalid subject data. Data deemed invalid due to protocol violations related to the UV exposure procedures such as subject moving during irradiation will count towards the maximum of 5 invalid subject data.

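### The AE exclusion for localised UV erythema has no exception for a stronger-than-expected reaction, so a marked burn confined to an irradiated sub-site is not captured as safety data

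*Protocol*

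**What the plan says.** Protocol section 2 measures the safety of the test product by "Frequency and severity of Adverse Events". SAP section 1.2 uses the same endpoint, and SAP section 1 bases general safety and tolerability on it.

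Protocol section 7.1.1 then lists what is not an AE. Items 1 and 2 each carry an exception; in item 2 it reads "unless more severe than expected for the subject's condition". Item 6 is "Localised erythema caused by exposure of the skin to UV radiation", with nothing after it. Section 6.5.4 restates the rule for the grading visit: "Localised erythema caused by exposure of the skin to UV radiation is expected and will not be reported as an adverse event". Sections 6.2.7, 6.3.4 and 6.4.5 say the same for Visits 2, 3 and 4.

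**The concern.** Leaving threshold erythema out of the AE record is sensible. It is the efficacy measurement, and section 9.2.2 rejects a subject's data when "The series of UV exposures on a subject fails to elicit an erythematous response on any sub-site, 16-24 hours after exposure". Every valid subject therefore has some erythema.

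The difficulty is at the other end of the scale. The design needs only first perceptible redness, but the exclusion also covers marked redness at the same spot. Because the safety objective is measured through AEs alone, a reaction of that kind would not appear in the safety tables. It would also carry no AE follow-up: sections 4.4 and 7.5 attach follow-up to AEs, and subjects are discharged at Visit 5, one day after the test irradiation.

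**Working it through.** No figure in the plan depends on this rule, so there is none to reproduce. The check compares the wording, looks for another record of intensity, and sizes the doses involved.

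**1. The exclusions side by side**

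| Protocol place | What is excluded | Exception for stronger than expected |
|---|---|---|
| 7.1.1, item 1 | Abnormal findings linked to the underlying disease | Yes, on the investigator's judgement |
| 7.1.1, item 2 | The condition being studied and its expected course | Yes |
| 7.1.1, item 6 | Localised UV erythema | None |
| 6.2.7, 6.3.4, 6.4.5, 6.5.4 | Localised UV erythema, described as expected | None |

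Item 2 does not clearly fill the gap. It concerns a disease or condition under study, the subjects are healthy volunteers (section 9.1), and item 6 is the more specific rule.

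**2. Is intensity recorded anywhere else?**

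- Grading (6.5.3) looks for the "lowest dose of UV radiation that produces the first perceptible unambiguous erythema". No intensity scale is defined, and the CRF takes MEDu and MEDp values.
- Section 9.2.2 rejects a series when "All sub-sites in the exposure series show an erythematous response 16-24 hours after exposure". That has an efficacy consequence, with no AE rule attached.
- SAP Listing 16.2.6 holds MED and SPFi values, validity and the reason for exclusion.
- SAP section 2.6 tabulates and lists AEs only.

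No planned record shows how strong the erythema was.

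**3. The dose ladder**

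Inputs: progression 1.25 and centring, from section 6.4.4 ("The dose of UV radiation administered to subjects will be chosen such that the expected MEDp will be irradiated on the 4th of the 6"); expected SPF 21 for the test product, from section 5.1. Six sub-sites are assumed, the stated minimum for protected sites.

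Relative dose at sub-site i = 1.25^(i − 4). In multiples of the provisional MEDu, the test-product site receives 21 times that.

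| Sub-site | 1 | 2 | 3 | 4 | 5 | 6 |
|---|---|---|---|---|---|---|
| Relative to expected MEDp | 0.512 | 0.640 | 0.800 | 1.000 | 1.250 | 1.5625 |
| Test site, × provisional MEDu | 10.8 | 13.4 | 16.8 | 21.0 | 26.25 | 32.8 |

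- Protection as expected: the top sub-site receives 1.25² = 1.56 times the expected MEDp. This equals the true MEDp multiple if protection is 21 and the provisional MEDu is correct.
- All six sub-sites respond: the lowest dose is at or above the true MEDp, so the top dose is at least 1.25⁵ = 3.05 times it. This bound follows from the ladder alone. Taking the provisional MEDu as correct, it corresponds on the test site to protection of 21 × 0.512 = 10.75 or less.

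**The case against.** The strongest reply is that the exclusion is narrow. It applies only to erythema that is localised and caused by UV, and the visit sections add that it is expected. Blistering, oedema and pain are not erythema and fall under the general definition in 7.1.1. Redness spreading past the irradiated spots is hard to call localised. A reaction the investigator judges to come from the product is not UV-caused, and signs of a suspected interaction are listed as AEs. Subjects are asked about symptoms at every visit (7.4), and section 7.1.2 leaves important medical events to medical judgement.

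Most of this stands. A reader might infer that no strong reaction under the test product, including a photo-reaction, can reach the safety endpoint. The documents do not support that, because item 6 turns on cause and location. Nor is the erythema row in SAP Tables 14.3.1.1 and 14.3.1.2 evidence of a conflict: it is a placeholder beside terms such as vomiting and dry mouth.

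Low protection is not hidden either. It shows as a low SPFi or a rejected result, and protocol section 12 requires rejected values to be reported. That is efficacy information, however, and says nothing about intensity.

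What the reply does not remove is the case of marked redness within the spot, attributed to UV, with no other sign or symptom. Calling it expected in the visit sections describes all such erythema; it does not set a limit. An event meeting a seriousness criterion could be argued to be reportable under 7.1.2, but that would not cover lesser burns.

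**Conclusion.** The concern holds in a limited form. Item 6 and four visit sections lack the exception that neighbouring items have, and no other safety measure fills the gap. Followed literally, marked erythema confined to an irradiated sub-site and attributed to UV is neither recorded nor followed up as an AE.

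The doses that bear on this are 1.56 times the expected MEDp at the top sub-site, and at least 3.05 times the true MEDp in the all-respond case that section 9.2.2 anticipates. These are dose multiples; they do not estimate how often, or how badly, anyone would burn. Larger multiples would need an assumed low protection that no document supports.

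The SPF estimate is unaffected. The point is a cheap improvement to what the safety endpoint captures.

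**What to change.** Align item 6 of section 7.1.1 and sections 6.2.7, 6.3.4, 6.4.5 and 6.5.4 with items 1 and 2: localised UV erythema is not an AE unless the investigator judges it more severe, more extensive or longer-lasting than expected. Where it is recorded, note the test site in the AE description. Listing 16.2.7.1 has no test-site column, so free text avoids changing the SAP shell.

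The change is one clause in five places and alters no dose, grading step or SPF calculation. The downside is a few more AE entries, among at most 25 randomised subjects. They would rest on investigator judgement, because the protocol defines neither an intensity scale nor an expected duration for the erythema.

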7.1.2. Serious Adverse Events

Serious Adverse Event is defined as any untoward medical occurrence that, at any dose:

A. Results in death

B. Is life-threatening NOTE: The term 'life-threatening' in the definition of 'serious' refers to an event in which the subject was at risk of death at the time of the event. It does not refer to an event, which hypothetically might have caused death, if it were more severe.

C. Requires hospitalization or prolongation of existing hospitalization NOTE: In general, hospitalization signifies that the subject has been detained (usually involving at least an overnight stay) at the hospital or emergency ward for observation and/or treatment that would not have been appropriate in the physician's office or out-patient setting. Complications that occur during hospitalization are AEs. If a complication prolongs hospitalization or fulfills any other serious criteria, the event is serious. When in doubt as to whether "hospitalization" occurred or was necessary, the AE should be considered serious.
 
Hospitalization for elective treatment of a pre-existing condition that did not worsen from baseline is not considered an AE.

D. Results in disability/incapacity NOTE: The term disability means a substantial disruption of a person's ability to conduct normal life functions.
 
This definition is not intended to include experiences of relatively minor medical significance such as uncomplicated headache, nausea, vomiting, diarrhea, influenza, and accidental trauma (e.g. sprained ankle) which may interfere or prevent everyday life functions but do not constitute a substantial disruption.

E. Is a congenital anomaly/birth defect

F. Other Situations
 
 1. Medical or scientific judgment should be exercised in deciding whether reporting is appropriate in other situations, such as important medical events that may not be immediately life-threatening or result in death or hospitalization but may jeopardize the subject or may require medical or surgical intervention to prevent one of the other

 GlaxoSmithKline	Document Name	207640 Protocol.doc		
	Type	Version	Document Identifier	Effective Date
	eldo_controlled	2.0; Most-Recent; Effective; CURRENT	090032d580d3df08	11-May-2017 13:45:31
	Reason For Issue	Auto Issue		

outcomes listed in the above definition. These should also be considered serious.

2. Examples of such events are invasive or malignant cancers, intensive treatment in an emergency room or at home for allergic bronchospasm, blood dyscrasias or convulsions that do not result in hospitalization or development of drug dependency or drug abuse or reports of spontaneous abortion.

